9.10 Adverse event follow-up

All AE should be followed until they are resolved, until the investigator assesses them as chronic or stable, or until the participant participation in the trial ends (i.e., until a final report is completed for that participant).

In addition, all SAE and non-serious events assessed by the investigator as possibly related to the investigational drug, must be followed even after the participant participation in the trial is over. Such events should be followed until they are resolved or until the investigator assesses them as “chronic” or “stable.”

9.11 Withdrawal criteria

A participant should be withdrawn from the trial treatment if, in the opinion of the investigator, it is medically necessary, or if it is the wish of the participant. If a participant does not return for a scheduled visit, every effort should be made to contact the participant.

In any circumstance, every effort should be made to document participant outcome.

If the participant withdraws consent, no further evaluations should be performed and no attempts should be made to collect additional data, except for safety data, which should be collected if possible and in accordance with participant consent.

If a participant withdraws from the trial, the reason must be noted on the CRF.

If a participant is withdrawn from the trial because of a treatment limiting AE, thorough efforts should be made to clearly document the outcome of AE.

9.12 Rules in case of treatment suspension or temporarily interruption

Treatment discontinuation does not automatically imply withdrawal from the trial. The duration of study medication interruptions will depend on each AE and is determined at the discretion of the investigator. The sum of the interruptions may not exceed 15 days. If the event exceeds 15 days, the study medication would be permanently withdrawn from the participant. Treatment can be resumed, according to the assessment of the trial investigator in charge of the participant, observing the instructions for safety assessment and follow-up as per section 6.9. These participants should continue with trial visits and assessments as planned, but the reasons for treatment discontinuation must be recorded in the

appropriate source documentation and CRF.

9.13 Rules for permanently interrupting trial treatment

The Investigator will permanently interrupt the treatment based on the following:

- ALT or AST >5x upper limits of normal (ULN) for more than two weeks;
- ALT or AST >3x ULN and Total bilirubin 2x ULN or International Normalized Ratio (INR) >1.5, known as Hy's law criteria, to be reported as a SAE;
- ALT or AST >3x ULN with the appearance of fatigue, nausea, vomiting, right upper quadrant pain or tenderness, fever, rash, and/or eosinophilia (>5%);
- AE or any other condition which, in the investigator's opinion, would put the participant at undue risk by continuing the trial treatment;
- Major protocol deviation incompatible with the continuation/participation on the trial;
- Any condition that the investigators consider medically necessary to interrupt the treatment, such as:
 - Significant leukopenia (<500 cells/mm³);
 - Severe gastrointestinal symptoms;
 - Severe allergic dermatopathy;
 - Peripheral sensitive neuropathy.
- Pregnancy.

Regardless of the reasons for trial treatment interruption, the investigator will make all necessary arrangements to ensure that the participant receives the appropriate treatment for the relevant medical condition. Rescue treatment will be offered for these participants, if appropriate, upon trial completion.

9.14 Lost to Follow-up

A participant will be considered lost to follow-up if they are unable to be contacted by the study team. The following actions must be taken if a participant fails to comply with required study procedures:

- The clinical trial team must attempt to contact the participant as soon as possible and counsel the participant on the importance of maintaining the assigned procedure schedule and ascertain whether the participant wishes to and/or should continue in the study or not.
- Before a participant is deemed lost to follow-up, the investigator or designee must make every effort to regain contact with the participant (where possible, three telephone calls and, if necessary, a certified letter to the participant's last known mailing address or local equivalent methods). These contact attempts should be documented in the participant's medical record.
- Should the participant continue to be unreachable, they will be considered to have withdrawn from the study with a primary reason of lost to follow-up.

10. Statistical Considerations

10.1 Sample Size Determination

A total sample size of 672 subjects (224 per trial arm, and 336 per country) will be necessary to achieve 90% power to detect a non-inferiority margin difference of 15%, assuming that the standard regimen failure rate is 10% and the intervention regimen is 12%, for a one-sided Z test at a significance level of 0.025. This total sample size has been increased in anticipation in 40% to assure a minimum 60% of participants with active infection (positive PCR) and further by 10% to account for potential losses to follow-up, in order to maintain the specified power and inferiority/superiority margins. This means that individuals removed from the study for the reasons mentioned will not be replaced. This sample size will allow the study to also demonstrate a superiority margin of difference of 10% with 80% power regarding the safety of the experimental arm. Considering the percentage of treatment interruption for conventional treatment of 20%, and a reduction of 50% in the experimental arm, power of 90% and $\alpha=0.05$, 197 patients will be needed in each arm.

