10.3 Statistical Analyses

Categorical variables will be presented as frequencies and percentages and continuous variables as median (interquartile range) or mean (standard deviation) according to the data distribution. Normality of distribution will be checked through histograms and the Kolmogorov-Smirnov test.

The chi-squared test or Fisher exact test will be performed to compare the frequencies across categorical variables and the Mann-Whitney test or Student t-test will be used to compare the continuous variables. Intention-to-treat analysis will be performed to evaluate the efficacy and safety that includes all participants randomized to the study groups. The primary analysis will compare proportion of patients with sustained negative PCR at 24 months in their randomly assigned treatment groups (intention-to-treat analysis). Moreover, the proportion of participants with adverse drug events will be also compared. Comparison analyses between groups will be performed using generalized linear models with a log-link

and binomial distribution. Longitudinal differences on quality-of-life scores between groups will be fitted using linear mixed models.

A per protocol analysis will also be performed. Those participants who do not comply with treatment or permanently interrupt or modify the proposed treatment will be excluded from the analysis unless they had a positive PCR prior to that time-point, in which case they will be included in the analysis and considered as a treatment failure.

For PCR analyses, means and bilateral 95% confidence intervals will be presented by group and visit. In addition, time to sustained parasite clearance until 6, 12, 18 and 24 months of follow-up visits will be assessed using Kaplan–Meier survival analysis with log rank test for significance. Repeated measures analysis will also be performed.

Statistical significance will be set at 0.025 for the non-inferiority outcome (positive PCR) and 0.05 for the superiority outcome (percentage of adverse drug reactions and QOL).

The interim analysis for early stopping will be based on superiority and conducted when all participants have reached 12 months of follow up since the end of treatment. An independent data and safety monitoring board (DSMB) will be convened for this study with expertise in CD, clinical trials as well as biostatistics. The purpose of the DSMB is to analyze the preliminary data at 12 months to help in the decision of interrupting any arm.

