10.9 Safety Analysis

Safety analyses will include all participants who have received at least one dose of the study medication. The proportion of participants with SAE, AESI and/or AEs leading to treatment discontinuation will be described per study arm and by System Organ Class (using preferred terms defined by MedDRA 13.1), according to the CTCAE, version 5. The proportion of participants presenting at least one AE will be described. Participants with multiple events with the same preferred terms will be counted once. The maximum severity grade for each preferred term and body system will be summarized. If multiple events with the same preferred terms are recorded for a participant, the event with the maximum grade will be

included in the analysis. In addition, a narrative for each of the SAEs and AESI will be developed detailing all aspects related to the medical event. AEs not leading to treatment discontinuation will also be described per study arm using the same classification as presented above.

Incidence rate and 95% confidence interval will be presented per study arm will be presented for SAE and AEs per category and most frequent AEs. Otherwise only descriptive statistics will be presented.

Safety laboratory parameters (hematology and biochemistry) will also be described individually per study arm, showing the proportion of participants by degree of elevation relative to ULN and to baseline values and clinical significance, and blood levels changes over time. Shift tables will be presented. A listing of participants experiencing lab parameters elevation will be included.

EKG abnormalities will be described per treatment arm as the proportion of participants per type of EKG finding, clinical relevance and changes over time. Participants with altered EKG may have an echocardiogram to evaluate cardiac involvement or cardiac progression of CD.

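### Section 10.1 attaches 90% power to 197 patients per arm for the safety comparison, but 197 is the 80% figure

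*Protocol*

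**What the plan says.** Section 10.1 plans 672 participants, 224 per arm, a number derived from the PCR non-inferiority comparison. It inflates the total for PCR positivity at baseline and for 10% losses, "in order to maintain the specified power and inferiority/superiority margins". Two statements about safety follow.

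- The planned size is said to allow the study to "demonstrate a superiority margin of difference of 10% with 80% power regarding the safety of the experimental arm".
- The next sentence gives its own inputs and result: "Considering the percentage of treatment interruption for conventional treatment of 20%, and a reduction of 50% in the experimental arm, power of 90" per cent, alpha 0.05, and "197 patients will be needed in each arm".

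Section 10.3 sets the significance level at "0.05 for the superiority outcome (percentage of adverse drug reactions and QOL"). It does not say whether that test is one- or two-sided. For categorical comparisons it states that "The chi-squared test or Fisher exact test will be performed", and it also names a log-link binomial model for comparisons between groups. Section 3 lists the safety endpoint as adverse events leading to treatment discontinuation, and the abstract says the same.

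**The concern.** A 50% reduction from 20% is 10%, so both safety sentences in section 10.1 concern a 10-point difference. One gives 80% power for the planned 224 per arm; the other gives 90% for a smaller number, 197. For the same pair of rates, power cannot be higher with fewer patients, so at least one figure is wrong.

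The trial aims to show that a short regimen is as effective as the standard one and safer. A safety comparison that fails to reach significance will be read against the stated power. A reader who trusts the 90% would put the chance of missing a true halving of interruptions at 10%.

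There is a lesser mismatch in wording. The parenthesis in section 10.3 attaches the 0.05 superiority test to adverse drug reactions, whereas the endpoint listed in section 3 is discontinuation because of adverse events, and section 10.1 sizes treatment interruption.

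**Working it through.** **Inputs.** Control 20%, short arm 10%, alpha 0.05 (section 10.1); equal allocation (section 6.6); one short arm compared with control, without multiplicity adjustment. The sidedness of the safety test is not stated, so both were tried.

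Variance sum: 0.20×0.80 + 0.10×0.90 = 0.16 + 0.09 = 0.25. Difference: 0.10.

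**Reproducing 197.** Unpooled formula: n per arm = (z_alpha + z_power)² × 0.25 / 0.10².

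- Two-sided 0.05, 80%: (1.960 + 0.842)² × 25 = 196.2, so **197**. This matches the protocol.
- Two-sided 0.05, 90%: (1.960 + 1.282)² × 25 = 262.7, so 263.
- One-sided 0.05, 80%: (1.645 + 0.842)² × 25 = 154.6, so 155.
- One-sided 0.05, 90%: (1.645 + 1.282)² × 25 = 214.1, so 215.

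**Other formulas.** With the pooled variance under the null (mean rate 0.15, 2×0.15×0.85 = 0.255), n = [z_alpha√0.255 + z_power√0.25]² / 0.10²:

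- Two-sided 80%: 199.0, so 199.
- Two-sided 90%: 265.9, so 266.
- One-sided 90%: 216.5, so 217.

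At 90% power, the continuity-corrected formula gives 286 two-sided and 237 one-sided, and the arcsine formula 261 and 213. The log risk ratio and log odds ratio formulas give 285 and 278 two-sided. The smallest 90% figure from any of these is 213, still above 197.

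**Power at the numbers that matter.** Power = Φ(0.10 / √(0.25/n) − z_alpha).

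| n per arm | Two-sided, formula | Two-sided, exact chi-squared | Two-sided, Fisher | One-sided, formula |
|---|---|---|---|---|
| 197 | 80.2% | 80.4% | 76.1% | 87.7% |
| 202 | 81.1% | 81.1% | 77.3% | 88.4% |
| 224 | 84.9% | 85.2% | 81.9% | 91.1% |

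For 197 two-sided: 0.10 / √(0.25/197) = 2.807; 2.807 − 1.960 = 0.847; Φ(0.847) = 0.802.

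The 202 is 224 × 0.9 = 201.6, because section 10.1 applies its loss allowance to the superiority margin as well. The 224 is the upper end because both sets named for safety keep patients who are lost later: section 10.3 says "Intention-to-treat analysis will be performed to evaluate the efficacy and safety that includes all participants randomized to the study groups", and section 10.9 says "Safety analyses will include all participants who have received at least one dose of the study medication".

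**Shortfall against 90%, two-sided.** 263 − 197 = 66 and 266 − 197 = 69 more per arm. The planned 224 is also below 263.

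**The case against.** The strongest reply has four parts.

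1. **Nothing turns on the figure.** The trial size is set by the efficacy comparison, safety is a secondary objective, and 224 exceeds 197. This stands as far as it goes: no patient number or analysis changes. The stated power is still wrong, and it is the benchmark for reading a null safety result.

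2. **The two sentences describe different things.** The 80% belongs to the planned sample of 224, and the 197 is a requirement with its own inputs. That is a fair reading, and it means the 80% sentence alone does not prove that 197 is an 80% number. The proof is that the formula returns 197 at 80%. The reading does not rescue the 90%, since it would give the smaller sample more power for the same difference.

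3. **A one-sided 0.05 test may have been meant.** Then 90% needs 215 to 217 per arm and 224 would reach about 91%, so the 90% could stand and the 197 would be the error. This cannot be excluded from section 10.1 alone. Against it, the one-sided 90% formulas do not give 197, the two-sided 80% formula gives it exactly, the preceding sentence also says 80%, and section 4.1 uses a two-sided 5% error rate for superiority at the interim analysis. Under either reading the sentence is wrong as printed.

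4. **The 81% to 85% range depends on choices.** Dividing by 1.1 instead gives 224/1.1 = 203.6, and power at 203 is 81.3%. A Wald test on the log risk ratio gives 80.2% at 202 and 84.7% at 224. The range barely moves. The allowance for baseline PCR positivity does not bear on a safety comparison in all randomised or all dosed patients.

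On the wording in section 10.3, that section also plans a separate comparison of adverse drug events, so the mismatch does not show that the wrong test is planned. The power correction does not depend on it.

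**Conclusion.** The stated 90% is wrong for 197 per arm at 20% versus 10%, whether alpha is one- or two-sided. The 197 is the 80% figure for a two-sided 0.05 test with unpooled variance. Two-sided power at 197 is 80.2%, so the risk of missing a true halving is about 20%, twice what the sentence implies.

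The planned size gives about 81% (202 per arm) to about 85% (224 per arm) for one short arm against control. By the chi-squared test the trial therefore meets its own 80% statement. With Fisher's exact test, which section 10.3 also allows, it would be 77.3% to 81.9%.

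These figures assume the protocol's rates of 20% and 10% and no multiplicity adjustment across the two short arms. That 80% two-sided was intended is an inference from the exact match and the adjacent sentence. The error itself is arithmetic and does not rest on that inference.

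**What to change.** In section 10.1, change the power given with the 197 from 90% to *80% (two-sided alpha 0.05)*. The two safety sentences then agree and the 197 reproduces. If the power of the planned size is also to be stated, give it as a range for one short arm versus control: about 81% with about 202 per arm after the 10% loss allowance, to about 85% with all 224.

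In section 10.3, replace adverse drug reactions in the parenthesis on the 0.05 superiority outcome with *AE leading to treatment discontinuation*, to match section 3 and the abstract. The place of quality of life in that parenthesis is a separate question and is left alone here.

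The cost is one figure and one phrase. No patients are added and the design is unchanged. What is given up is the claim of 90% power for safety; keeping that claim with a two-sided test would take 263 to 266 per arm.

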10.2 Populations for Analyses

For analysis purposes, the following populations are defined and will be described in greater detail in the trial Statistical Analysis Plan:

Population	Description
Intention to Treat (ITT)	All enrolled participants who are randomized into the study.
Per Protocol	All patients completing the study without major protocol deviations. Patients with a positive PCR result prior to time of exclusion, will be included and considered as treatment failure.
Safety population	All subjects who received at least one dose of study medication.

10.3 Statistical Analyses

Categorical variables will be presented as frequencies and percentages and continuous variables as median (interquartile range) or mean (standard deviation) according to the data distribution. Normality of distribution will be checked through histograms and the Kolmogorov-Smirnov test.

The chi-squared test or Fisher exact test will be performed to compare the frequencies across categorical variables and the Mann-Whitney test or Student t-test will be used to compare the continuous variables. Intention-to-treat analysis will be performed to evaluate the efficacy and safety that includes all participants randomized to the study groups. The primary analysis will compare proportion of patients with sustained negative PCR at 24 months in their randomly assigned treatment groups (intention-to-treat analysis). Moreover, the proportion of participants with adverse drug events will be also compared. Comparison analyses between groups will be performed using generalized linear models with a log-link

and binomial distribution. Longitudinal differences on quality-of-life scores between groups will be fitted using linear mixed models.

A per protocol analysis will also be performed. Those participants who do not comply with treatment or permanently interrupt or modify the proposed treatment will be excluded from the analysis unless they had a positive PCR prior to that time-point, in which case they will be included in the analysis and considered as a treatment failure.

For PCR analyses, means and bilateral 95% confidence intervals will be presented by group and visit. In addition, time to sustained parasite clearance until 6, 12, 18 and 24 months of follow-up visits will be assessed using Kaplan–Meier survival analysis with log rank test for significance. Repeated measures analysis will also be performed.

Statistical significance will be set at 0.025 for the non-inferiority outcome (positive PCR) and 0.05 for the superiority outcome (percentage of adverse drug reactions and QOL).

The interim analysis for early stopping will be based on superiority and conducted when all participants have reached 12 months of follow up since the end of treatment. An independent data and safety monitoring board (DSMB) will be convened for this study with expertise in CD, clinical trials as well as biostatistics. The purpose of the DSMB is to analyze the preliminary data at 12 months to help in the decision of interrupting any arm.

A control event rate is expected to be 10% of treatment failure (at least one positive PCR during follow up period) and a 20% of treatment withdrawn due to any AE. Control arm showing posterior probability of superiority of 97.5% or higher will be considered superior. This will be calculated for the experimental intervention versus the control group based on the observed data at the time of interim assessment with a superiority p-value stopping boundary of 0.010.

The decision for interim analysis will be made in a blinded manner (e.g., based on pooled number of events).

All analyses will be performed using Stata 13.0 for Windows.

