In this international, multicenter, double-blind, phase III, placebo-controlled study, 672 participants will be randomly assigned to receive the standard-dose of benznidazole (300 mg daily for 8 weeks) or the short experimental regimens (benznidazole 300 mg daily for the first 2 weeks plus placebo for the last 6 weeks or benznidazole 300 mg daily for the first 4 weeks plus placebo for the last 4 weeks). Efficacy will be assessed considering a non-inferiority design and through the detection of parasite deoxyribonucleic acid (DNA) through molecular biology (Polymerase Chain Reaction - PCR). Meanwhile, safety will be evaluated through a superiority design, with the aim to find the new regimen as effective as the standard one, but superior in terms of safety. An intention-to-treat analysis will be performed, and statistical significance will be set at 0.025 for the non-inferiority outcome (positive PCR) and 0.05 for the superiority outcome.

The study population will be adult participants, 18 years or older, with chronic Chagas disease in its indeterminate or mild cardiac forms, with a positive diagnosis from two serological assays. The trial will be conducted in four sites: two in Bolivia, and two in Colombia. The primary endpoint will be parasitological response determined as sustained negative qualitative PCR at 24 months after treatment. The proportion of participants with positive qualitative PCR will be measured at 1, 4, 6, 8, 12, 18, and 24 months from end of treatment. The frequency of adverse events leading to treatment discontinuation will be compared. An economic evaluation will be conducted assessing the direct and indirect costs, including procedures associated with the management of adverse events.

Key words

Chagas disease, treatment, short regimen, benznidazole.

1. Rationale and background information

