5.1 Eligibility criteria

5.1.1 Inclusion Criteria

- Adults aged ≥ 18 years;¹
- CD diagnosis through the positivity of two serological tests that use different antigens (recombinant and native antigens, according to World Health Organization (WHO) recommendations) (28).
- Informed consent form read and signed by the participant.
- Weight ≥ 50 kg to ≤ 95 kg.
- Ability to carry out all tests and visits to the protocol site and have a fixed address.
- Women of childbearing age should have a negative urine or serum pregnancy test at baseline.

¹ It is considered that neither the dynamics of parasitemia, nor the therapeutic response and safety profile, demonstrate differences in the chronic phase adult population up to 60 years of age. Considering that there is no contraindication for administering antiparasitic treatment beyond 60 years of age, and that the objective is to see the antiparasitic effect and the safety profile, recruiting patients older than 60, which will allow a greater probability of recruiting patients in the shortest possible time, optimizing studytimes, financial resources, and the opportunity to have the results available.

A contraceptive method should be used.²

Note that although PCR will be determined at baseline, this will not be considered as an inclusion criterion.

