8.1 Screening visit

The centers chosen to participate in the study are already considered reference centers for the treatment of Chagas disease. Each center has its own patient referral flows framed within each health system. The doctors who treat the patients themselves who will offer them the possibility of participating in the clinical trial as long as they meet all the inclusion criteria and none of the exclusion criteria.

During screening, the following assessments will be done to evaluate participant eligibility for the study:

- Signature after reading the Informed Consent Form;
- Complete medical history with an emphasis on CD;
- Demographic data, history of medications and toxic habits;
- Physical examination, body weight/height and vital signs;
- CD serology: serum sample will be documented at screening for conventional CD serology. Participant must have at least 2 positive tests to be eligible;
- Real-time PCR collected for quantitative assessment for all participants (result is not required for randomization);
- Clinical safety laboratory evaluations (whole blood and serum sample): hemoglobin, total white blood cells (WBC) count, differential WBC count, numerical platelet count, ALT, AST, urea, creatinine;
- Serum pregnancy test: women of reproductive age will undergo a serum pregnancy test at screening. The test must be negative for the woman to be considered eligible for this study;
- EKG: will be obtained at screening. Participants with abnormal EKGs will undergo an echocardiogram.

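### The sample size is built on about 122 baseline PCR-positive participants per arm, but the primary non-inferiority test covers everyone randomised, up to 40% of whom may be PCR-negative at baseline

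*Protocol*

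**What the plan says.** Section 10.1 assumes 10% failure on the standard regimen and 12% on a short one, a 15-point margin, one-sided 0.025 and 90% power. It arrives at 224 per arm (672 in total). The number was "increased in anticipation in 40% to assure a minimum 60% of participants with active infection (positive PCR") and raised by a further 10% for losses, with the aim of keeping the stated power and margins. It adds that "individuals removed from the study for the reasons mentioned will not be replaced".

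The analysis sections say something else:

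- Section 10.2 defines ITT as "All enrolled participants who are randomized into the study". The other two sets are per protocol and safety. None depends on baseline PCR.
- Section 10.3: "The primary analysis will compare proportion of patients with sustained negative PCR at 24 months in their randomly assigned treatment groups (intention-to-treat analysis").
- Abstract: "An intention-to-treat analysis will be performed, and statistical significance will be set at 0.025 for the non-inferiority outcome (positive PCR").
- Section 5.1.1: "Note that although PCR will be determined at baseline, this will not be considered as an inclusion criterion".
- Section 10.3 defines failure as "at least one positive PCR during follow up period".

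**The concern.** Sections 10.1 and 10.2/10.3 describe two different primary analyses. The first inflates the sample so that enough PCR-positive participants remain, and speaks of people being removed. The second removes nobody on the ground of baseline PCR.

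The choice matters because of the endpoint. Someone who is PCR-negative before treatment and stays negative is a success whichever regimen was given. To the extent that this happens equally in all arms, it pulls the arms together. In a superiority trial that costs power. In a non-inferiority trial it makes an inferior regimen easier to pass. Section 10.4 says the margin is meant to be conservative, to avoid wrongly concluding that a new regimen is effective, and section 21 intends the results to support label changes. As written, a reader cannot tell which population the 15 points protects.

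**Working it through.** **1. Reproducing the plan's figure.** Inputs from section 10.1: failure 0.10 and 0.12, margin 0.15, one-sided alpha 0.025 (z = 1.960), power 90% (z = 1.282).

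n per arm = (1.960 + 1.282)² × (0.10×0.90 + 0.12×0.88) / (0.15 − 0.02)² = 121.6, so 122.

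122 / 0.6 × 1.1 = 223.7, so 224 per arm and 672 in total, which is the stated figure. Reading the 40% as a multiplier does not fit: 122 × 1.4 × 1.1 = 188. The 122 are therefore PCR-positive participants.

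Cross-check: the same inputs applied to everyone randomised would give far more than 90% power. With n = 202 per arm (224 less 10%), SE = √((0.0900 + 0.1056)/202) = 0.0311 and power = Φ(0.13/0.0311 − 1.96) = 98.7%. With n = 224 it is 99.3%.

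**2. What the margin means among PCR-positives.** Let f be the PCR-positive share. If negatives fail at the same rate in every arm, whatever that rate is, the all-randomised difference equals f times the difference among positives. The margin among positives is then 0.15/f: 25.0 points at f = 0.6, 21.4 at 0.7, 18.8 at 0.8 and 16.7 at 0.9.

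**3. Chance of declaring non-inferiority when a short regimen is 15 points worse among positives (10% v 25%).** Let qc and qe be the failure rates among negatives on control and short regimen. These are assumptions, since the protocol gives none.

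pc = f×0.10 + (1−f)×qc; pe = f×0.25 + (1−f)×qe; d = pe − pc

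P = Φ((0.15 − d)/SE − 1.96), SE = √((pc(1−pc) + pe(1−pe))/n), with n = 202 or 224.

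Example with f = 0.6, qc = qe = 0 and n = 202: pc = 0.06, pe = 0.15, d = 0.09, SE = 0.0302, P = Φ(0.06/0.0302 − 1.96) = 51%.

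| PCR-positive share | Negatives fail equally, 0–10% | Negatives 5% v 12.5% | Negatives fail like positives (10% v 25%) |
|---|---|---|---|
| 60% | 41–55% | 14–15% | 2.5% |
| 70% | 25–31% | 9–10% | 2.5% |
| 80% | 13–15% | 6% | 2.5% |
| 90% | 6% | 4% | 2.5% |

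Ranges cover n = 202 to 224. Simulation (400,000 runs per case, Wald test) agrees within about 1.5 percentage points.

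**4. Power if the test is run on PCR-positives.** At 60% positive, 224 × 0.6 = 134 per arm, or 121 after 10% losses. With 10% v 12% failure and a 15-point margin, power is 92.5% and 89.9%.

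**5. Power if all randomised is kept with an equivalent margin.** At f = 0.6 and equal failure among negatives, 15 points among positives becomes 0.6 × 15 = 9 points overall. With 10% v 12% among positives and 202–224 per arm, power is 88–91% if negatives never fail, 80–84% at 5% failure and 72–76% at 10%.

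**The case against.** **Type I error is kept for the hypothesis as written.** Section 10.4 states the margin as a difference in failure rate and does not limit it to PCR-positives. For 15 points among all randomised the test holds 2.5%. This stands: the 41–55% is the chance of passing when the PCR-positive part is 15 points worse, not a breach of the literal null. But section 10.1 sized the trial for that part, and section 10.4 makes no allowance for negatives.

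**The size depends on a rate nobody states.** Everyone enrolled is seropositive, untreated infection is described as lifelong, baseline status rests on one screening sample, and failure is any positive over seven follow-up samples. Some baseline negatives may turn positive, perhaps more often after shorter treatment. This also stands, which is why the results are a range. The dilution vanishes only if negatives fail exactly like positives. Conversely, nothing in eligibility or randomisation enforces the 60%, so 25 points is not an upper limit.

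**The SAP may settle it.** Section 10.2 defers further detail of the populations, and the remark in 10.1 about removed individuals may hint at a PCR-positive set. But section 10.3 already fixes the primary set, so an SAP that restricted it would contradict the protocol.

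**All randomised is a defensible target.** Eligibility is by serology and the stated aim is public health. That is a legitimate choice, but the sample size and margin must then be argued for that population.

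**Conclusion.** The protocol contradicts itself on the population for its primary test, and the version that governs the analysis favours the short regimens. The conflict follows from the protocol's own figures and needs no assumption. Its effect does: the 25-point margin assumes 60% positive and no arm difference among negatives, and the false-pass probabilities depend on the unknown failure rate among negatives. Only the case in which baseline PCR makes no difference to failure leaves the nominal 2.5% intact among the participants for whom the trial was sized. Because this decides what a non-inferiority claim would mean, it must be resolved before the analysis.

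**What to change.** In section 10.2 add a primary efficacy set: all randomised participants with a positive screening PCR, analysed in the arm assigned. Name it as primary in 10.3, 10.8 and the abstract, and restrict the per-protocol efficacy set in the same way. Keep all-randomised ITT as a supporting efficacy analysis and leave the safety population unchanged. Section 8.1 provides the data: "Real-time PCR collected for quantitative assessment for all participants (result is not required for randomization"). The sample precedes randomisation and section 7 keeps the laboratory blinded, so restricting on it does not break the randomised comparison.

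The objectives table, the interim analysis and section 10.11 (which counts all 672 participants) should be aligned.

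Cost: wording only, with no extra patients, visits or samples. The primary analysis would use about 121–134 rather than 202–224 per arm at 60% positive, as section 10.1 already planned, and more if the positive share is higher. The restricted per-protocol set is smaller. Applying the 20% and 10% interruption rates of section 10.1 leaves about 97–107 control and 109–121 short-regimen participants, with 85–88% power.

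Alternative: keep all randomised as primary and rewrite sections 10.1 and 10.4 for that population, with a margin justified for the mixed population and an explicit assumption about failure among PCR-negatives. The 9-point equivalent keeps power near 90% at the present size only if negatives never fail.
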